#### 8.8.2.11. Laboratory Evaluations

Laboratory evaluations will include the tests listed in Appendix 1.

## 9. STUDY DRUG MATERIALS AND MANAGEMENT

#### 9.1. Study Drug

#### Table 4:Study Dug Information

Investigational Drug:	MN-001
Formulation:	250 mg tablet
Frequency:	250 mg qd or 250 mg bid
Storage Conditions:	Store at room temperature

## 9.2. Study Drug Packaging and Labeling

At a minimum the following information will be included on each bottle:

- Name of Sponsor
- Study number/Acronym/IND number
- Route of administration
- Quantity of dosage unit
- Directions for use
- Storage conditions
- Space for information to be completed by Investigator/designee:
  - Name and telephone number of Investigator
  - Dispensing date
  - Subject number
- Statement "Caution: New Drug Limited by federal law to investigational use"
- Statement: "Keep out of reach of children"

#### 9.3. Study Drug Storage

The clinical study drug MN-001 should be stored at room temperature (preferably 18-23oC, but 15-25oC is acceptable).

#### 9.4. Study Drug Administration

The study drug will be dispensed by appropriately qualified site study staff as indicated on the delegation of authority log. Subjects will self-administer the study drug at home except on scheduled visits to the clinic. On those days, subjects will wait until they come to the clinic to take their study medication. The subject will be instructed to return all unused study drug to the clinical trial site at each visit.

## 9.5. Study Drug Accountability

Investigational clinical supplies must be received by the PI or a designated person at the study site, handled and stored safely and properly, and kept in a secured location to which only the Investigator and/or designated assistants have access. Clinical supplies are to be dispensed only in accordance with the protocol.

The PI or designee is responsible for keeping accurate records of the clinical supplies received from the Sponsor or designee, the amount dispensed to and returned by the subjects, and the amount remaining at the conclusion of the study. At the end of the study, all clinical supplies must be returned to the Sponsor, or designee, after confirmation with the CRA (Clinical Research Associate) or destroyed at the clinical site. Study drug will not be destroyed until written documentation is received from the study sponsor or designee. Proper documentation of the destruction of study drug must be provided by the site.

The following information is to be included in the CRF: visit medication dispensed, dosing start/stop dates, dosage level, number of tablets dispensed and number of tablets returned.

# **10. ASSESSMENT OF EFFICACY**

#### **10.1. Primary Endpoints**

The primary endpoint, cholesterol efflux, will be calculated as the percent of cholesterol removed from the cells and appearing in the culture medium normalized to a reference serum pool. The ability of serum HDL to remove cholesterol from cultured cells will be assessed as an *in vitro* method to evaluate functional changes in HDL mediated by changes due to MN-001 treatment.

Cholesterol efflux with HDL will be measured by Cholesterol Efflux Fluorometric Assay Kit (BioVision, Inc.). Detailed protocol is attached in Appendix 3.

An additional primary endpoint is will evaluate the effects of MN-001 on triglyceride level in subjects with NAFLD or NASH. The primary endpoint will be decreased triglycerides measured as the difference after 12 weeks of treatment from baseline levels. The data are expressed as the percent change from the baseline value and calculated using he equation: Change = [100%\*(Endpoint value - Baseline Value)/Baseline Value]

#### **10.2.** Secondary Endpoints

Safety will be assessed by the monitoring and recording of all AEs and serious adverse events (SAEs), regular monitoring of hematology, blood chemistry and urine values, regular measurement of vital signs, electrocardiograms (ECGs), and the performance of physical examinations.

Other secondary measures, lipid profile including HDL-C, LDL-C, total cholesterol level, liver enzymes and percentage of fat in the liver assessed, will be measured by the change from baseline to Week 12.

Pharmacokinetic parameters of MN-001 and its metabolite, MN-002 will be calculated in a subset of 6 subjects.

# 11. ASSESSMENT OF SAFETY

Safety will be assessed by the proportion of subjects with the following events:

- clinical and laboratory treatment emergent adverse events (TEAEs)
- discontinuations due to TEAEs
- treatment emergent serious adverse events (TESAEs)

Safety (relationship and severity) and tolerability will further be assessed by statistical and clinical review of AEs, laboratory values, ECGs, physical examinations, vital signs and weight.

# **12. ADVERSE EVENTS**

## **12.1.** Definition of Adverse Events

An AE is any untoward medical occurrence in a study subject administered a medicinal (investigational) product and which does not necessarily have a causal relationship with this treatment. An AE can therefore be any unfavorable and unintended sign (including a clinically significant abnormal laboratory finding), symptom, or disease temporally associated with the use of a medicinal (investigational) product, whether or not considered related to the medicinal (investigational) product. Adverse events may include the onset of a new illness and the exacerbation of pre-existing conditions.

Other untoward events occurring in the framework of a clinical study are also to be recorded as AEs, (e.g., those occurring during treatment-free periods, including screening or post-treatment follow-up periods), in association with study-related procedures and assessments.

#### 12.2. Assessment of Adverse Events

The PI or an authorized physician will assess all AEs for severity, relationship with study medication, and whether it meets the criteria for classification as a SAE, requiring immediate notification to the Sponsor or designee (see Section 12.5). These assessments will be made in accordance with the standard ratings detailed in the following sections.

#### 12.2.1. Severity Assessment

The severity of AEs will be determined as described in Table 5.

Table 5:Adverse Events Severity Definition

Mild Grade 1	Ordinarily transient symptoms that do not influence performance of subject's daily activities. Treatment is not ordinarily indicated.
Moderate Grade 2	Marked symptoms sufficient to make the subject uncomfortable. Moderate influence on performance of subject's daily activities. Treatment may be necessary.
Severe Grade 3	Symptoms cause considerable discomfort. Substantial influence on subject's daily activities. May be unable to continue in the study and treatment may be necessary.
Life- threatening Grade 4	Extreme limitation in activity, significant assistance required; significant medical/therapy intervention required hospitalization probable.
Death Grade 5	Death.

When changes in the intensity of an AE occur more frequently than once a day, the maximum intensity for the event should be noted for that day. Any change in severity of signs and symptoms over a number of days will be captured by recording a new AE, with the amended severity grade and the date (and time, if known) of the change.

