### Phase 1 Studies

In the single dose studies of 80 mg to 600 mg, there appeared to be few adverse events. The most common treatment emergent adverse events (TEAEs) were mild diarrhea, sensation of borborygmus, and heavy headedness. No clinically significant changes in vital signs, ECGs, and safety labs were observed.

In two multiple dose studies (study KCA-757 and study 478-02), MN-001 250 mg to 1000 mg bid was administered for approximately 7 days in healthy volunteers and subjects with mild bronchial hypersensitivity. No serious adverse events were reported and no subjects discontinued the study due to an adverse event. The most common AEs experienced in study 478-02 were upper abdominal pain (reported by 1 subject each in the 500 mg and 750 mg groups), loose stools (reported by 1 subject each in the 500 mg and 1000 mg groups), and nausea (reported by 1 subject each in the 750 mg and 1000 mg groups). The Investigator considered the following treatment-emergent AEs to be possibly or probably related to study drug (treatment group in parentheses): abdominal pain (placebo), upper abdominal pain (500 mg and 750 mg), dyspepsia (1000 mg), fatigue (placebo), loose stools (500 mg and 1000 mg), nausea (750 mg and 1000 mg), somnolence (750 mg), urine odor abnormal (500 mg).

In study 478-02, vital signs were within normal limits. All mean ECG measurements remained within normal limits. At Hour 359.67 mean QTc for the 750 mg group increased 27.66 ms from baseline for a mean QTc of 395.83 ms and mean heart rate increased 14.50 bpm from baseline for a mean heart rate of 70.67 ms. No other marked mean changes from baseline were noted. The Investigator did not consider any of the ECG abnormalities in this study to be adverse events.

All treatment groups, including the placebo group, exhibited notable mean increases in CPK (ranging between 22 to 135 U/L) at Hour 360. No other marked mean changes from baseline were noted for the remaining serum chemistry parameters.

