#### 8.8.2.6. Electrocardiogram (12-Lead ECG)

All subjects will have standard resting 12-lead ECGs performed and interpreted. Subjects are to be supine for at least 5 minutes prior to ECG assessments. The time the ECG is performed will be recorded (using a 24-h clock).

The PI or a qualified designee listed on Form Food and Drug Administration (FDA) 1572 must review, initial, and date the report, which must be filed in the subject's study chart. Clinically significant findings at screening must be captured in the medical history. Any clinically significant changes compared post study drug administration must be captured as an adverse event in the CRF.

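### Table 5, the only AE severity scale, uses no measured value, so a large asymptomatic laboratory or ECG adverse event can be graded mild or severe

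*Combined protocol and SAP*

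**What the plan says.** Protocol 12.1 counts as adverse events unfavorable signs "including a clinically significant abnormal laboratory finding". For ECGs, 8.8.2.6 says "Any clinically significant changes compared post study drug administration must be captured as an adverse event in the CRF". Under 12.2, "The PI or an authorized physician will assess all AEs for severity", using the ratings set out in the sections that follow. The only severity rating there is in 12.2.1: "The severity of AEs will be determined as described in Table 5".

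Table 5 has five grades. Grade 1 covers passing symptoms with no effect on daily activity and adds "Treatment is not ordinarily indicated". Grade 2 covers marked symptoms with a moderate effect on activity and possible treatment. Grade 3 covers considerable discomfort with a substantial effect on activity and adds "May be unable to continue in the study and treatment may be necessary". Grade 4, labeled life-threatening, reads "Extreme limitation in activity, significant assistance required; significant medical/therapy intervention required hospitalization probable". Grade 5 is death.

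SAP 13.1 reports subjects as mild, moderate, severe or life-threatening, counting each subject at the worst grade reached for a given event. SAP Table 14.3.1.3 presents this by system organ class, preferred term and intensity. The SAP adds no grading criteria.

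**The concern.** The protocol asks physicians at several centers to give a severity grade to events that may have no symptoms, using a scale worded mainly by symptoms. A high transaminase or a long QTc can be clinically important while the subject feels well and carries on as usual. On such an event the clauses of Table 5 can point to different grades, and the protocol does not say which clause decides.

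What is at stake is the meaning of the severity table. Protocol section 11 makes laboratory as well as clinical treatment-emergent events a safety measure and says severity will be assessed. Protocol 13.1.3 says the results will be used to design later studies. If one site records a large asymptomatic abnormality as mild and another records the same abnormality as severe, the by-intensity table cannot be read at face value for that kind of event.

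**Working it through.** The plan states no figure on this point and no formula applies. The check is a reading of every place where severity, laboratory values or ECGs are graded, acted on or reported.

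1. **Are laboratory and ECG findings graded on Table 5?** Yes. Sections 12.1 and 8.8.2.6 make them adverse events when clinically significant, 12.2 requires all adverse events to be graded, and 12.2.1 names Table 5.

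2. **Does any grade use a measured value?** Going through the five: symptoms, activity and treatment (Grade 1); symptoms, activity and treatment (Grade 2); discomfort, activity, continuation and treatment (Grade 3); activity, assistance, intervention and hospitalization (Grade 4); death (Grade 5). Count: 0 of 5. By contrast, all five categories of Table 6, the causality scale, expressly include laboratory abnormalities. The protocol expects such events but gives no value-based way to grade them.

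3. **Is another scale invoked?** No. CTCAE is in the section 3 abbreviation list and nowhere else. The numeric limits elsewhere serve other purposes: 8.6.2 triggers retesting, 8.6.3 stops drug, and the QTcF limit in 7.2.2 excludes at entry.

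4. **Worked example.** A subject with baseline ALT below 2 times ULN has an asymptomatic rise to more than 5 times baseline, so 8.6.3 requires study drug to stop.
   - By symptoms and activity: no symptoms and no effect on activity, so Grade 1.
   - By continuation: 7.3 requires withdrawal when an abnormal laboratory test requires stopping the drug, which matches "May be unable to continue in the study and treatment may be necessary", so Grade 3.
   - Against that, 8.6.3 keeps such a subject on scheduled assessments while dosing is withheld and allows resumption case by case, so it is arguable whether the subject is unable to continue.
   - The treatment clauses do not settle it. Grade 1 says treatment is ordinarily not needed; Grades 2 and 3 both say it may be needed, so this clause cannot separate moderate from severe.
   
   Result: two grades apart, 1 against 3, both defensible from the text.

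5. **Where does the grade go?** Into SAP Table 14.3.1.3. Because the worst grade is taken within a specific event, a different reading moves a subject within that preferred-term row. It does not reset the subject's overall severity.

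6. **Does a stopping decision use the grade?** The individual grade-based stops in 7.3.1 concern nausea, diarrhea, vomiting and abdominal pain, which Table 5 can grade. The liver stops in 8.6.3 are numeric and ignore the grade. The study stop in 7.3.2 uses Grade 4 for two subjects with drug-related events, and describes it as life-threatening consequences needing urgent intervention. Table 5 describes the same grade as "Extreme limitation in activity, significant assistance required; significant medical/therapy intervention required hospitalization probable". The synopsis rule gives no description. Both descriptions are headed life-threatening, but they are not the same test.

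**The case against.** The best case against is that little depends on the gap. Liver safety is protected by numeric limits, and retesting and hepatologist observation begin at lower levels under 8.6.2. The medical monitor reviews Grade 4 cases with the PI before any decision to terminate, and 7.3 lets the sponsor stop the study at any time. The SAP plans laboratory summaries, shift tables and an abnormal-QTc table, so the values remain visible whatever grade is recorded. All of this stands, and it confines the point to descriptive severity reporting. The laboratory tabulation is only a partial substitute, since protocol 13.1.4 sets no cut-off for a markedly abnormal change.

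It is also fair to say that a physician who has stopped the drug and ordered repeat tests would be unlikely to choose mild. The Grade 1 against Grade 3 split is the extreme case. It remains a reading that the text allows.

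Three stronger readings are tempting and are not supported.

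- **A QTc risk.** In study 478-02, "At Hour 359.67 mean QTc for the 750 mg group increased 27.66 ms from baseline for a mean QTc of 395.83 ms", and a reader might add that rise to the 450 ms entry limit. That sum adds a group mean change to an individual limit and predicts nothing. The dose was 750 mg bid, three times this trial's top daily dose (1500 / 500 = 3). Mean ECG values stayed within normal limits, no other marked mean change was noted although 1000 mg bid was also tested, and MN-001-CL-003 found no clinically significant ECG change at 1500 mg/day. Hour 359.67 is about day 15 (359.67 / 24 = 14.99), while dosing lasted 6 or about 7 days. The time origin is not given, so it is not established that this was an on-drug reading.
- **A percentage distortion of the severity table.** Any such figure would be an assumed count divided by the sample size. The documents give no event rate.
- **A failure of the study stopping rule.** The two Grade 4 descriptions differ, but no case with conflicting results is shown, and monitor review comes before termination.

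Nor is the list of severities in protocol 13.1.4, which omits life-threatening, a live problem: SAP 13.1 supplies it.

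**Conclusion.** The point holds as a minor defect in the grading rule. Table 5 is the only scale for all adverse events, 0 of its 5 grades use a measured value, and an asymptomatic laboratory or ECG abnormality can be recorded as mild or severe depending on the clause chosen. The by-intensity table may understate such events or report them inconsistently across sites. The protocol adopts no value-based scale, so no correct grade is defined against which to measure error. The claim is that the text permits two grades and that one of them labels a large abnormality mild.

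The effect stops at descriptive severity reporting. The conclusion rests on two assumptions: that such events occur and are judged clinically significant, and that no grading instruction outside these documents fills the gap. Neither a QTc risk figure nor a percentage shift is claimed.

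**What to change.** In 12.2.1, keep Table 5 for symptomatic events. Have the investigator grade laboratory and ECG adverse events from the measured value on a named CTCAE version, relative to baseline where baseline is abnormal. State that the central or local result may be used, since 8.6.2 and 8.6.3 allow local testing for remote subjects. State also that this grade is the recorded severity, so that it does not compete with a separate physician rating under 12.2.

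Use the 7.3.2 description of Grade 4 as the single definition for the study stopping rule in the synopsis, 7.3.2 and Table 5. An isolated asymptomatic value then counts toward the two-subject rule only if it meets that description.

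The cost is protocol wording and a grading instruction to sites, plus some programming if the sponsor wants grades checked against central-laboratory values. No visits or samples are added. The downside is that some laboratory events will be reported at higher grades. The change does not touch the prior judgment of whether a finding is clinically significant, and ECG differences between sites may persist because no central ECG reading is described.

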## 13.1.4 Safety Analysis

Safety analyses will be conducted on the Safety Analysis Set.

The incidence of treatment-emergent AEs (TEAEs, defined as AEs occurring from the time of first dose through 7 days after the last dose of study medication), SAEs and AEs leading to discontinuations will be summarized by treatment group. Incidence of TEAEs will also be summarized by severity (mild, moderate, or severe), as well as by relationship to treatment (not related, possibly related, or probably related) and by seriousness.

Changes from baseline in laboratory values will be summarized for continuous variables. Lab shift tables showing incidence of new or worsening clinically significant findings from baseline to the last visit will be displayed. Shift from baseline to the highest lab value, and from baseline to the lowest lab value will also be displayed.

Incidence of out-of-normal-range values and markedly abnormal change from baseline in laboratory safety test variables will be tabulated.

Changes in vital signs from baseline to each visit will be summarized by treatment groups.

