### DEFINITIONS

Adverse Event	An adverse event (AE) is any untoward medical occurrence in a subject administered a pharmaceutical product, regardless of causality assessment.		
Full Analysis Set Population	Group of randomized subjects who received at least 14 days of study drug and had at least one post-dose efficacy measurement.		
Safety Analysis Set Population	Group of subjects who received at least one dose of study drug and had at least one post-dose safety assessment.		
PK population	PK sample collection of the first 6 subjects enrolled in the study.		
Serious AE	An AE occurring at any dose that: results in death; is a life-threatening experience; requires inpatient hospitalization or prolongation of an existing hospitalization; results in a persistent or significant disability/incapacity; or is a congenital anomaly/birth defect in the offspring of a patient who received study drug.		
Treatment- emergent AE	AEs occurring from the time of first dose through 7 days after the last dose or that is already present prior to the first dose of study drug and becomes more severe post-dose		

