## 13.1 Adverse Events

All AEs occurring after the subject signed Informed Consent Form (ICF) will be reported and will be coded using the latest version of MedDRA dictionary.

An overall summary of the number and percentage of subjects with AEs, subjects that lead to discontinuation of study drug, AEs related to study drug (the relationship will be categorized as "related" or "unrelated", where "related" includes investigator terms of "Possibly Related" and "Probably Related"), SAEs, and SAEs related to study drug will be presented by treatment. Also, the AEs will be presented by SOC, PT and treatment. In addition, subjects with AEs in various severity categories (mild, moderate, severe, and life-threatening) will be presented based on the maximum severity of a specific AE for a subject.

Listings of individual by-subject data for any subject experiencing an SAE will be provided separately. All AEs will also be presented in individual by-subject data listings.

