# **15 TABLES AND LISTINGS**

### 15.1 Table of Tables

Table Number	Table Description		
14.1	Demographic Data		
14.1.1	Subject Disposition (including discontinued subjects)		
14.1.2	Summary of Protocol Deviations		
14.1.3	Demographics and Baseline Characteristics		
14.1.4	Summary of Medical History		
14.1.5	Prior and Concomitant Medications (Safety Population)		
14.1.6	Study Drug Exposure		
14.2	Efficacy		
14.2.1	Summary of Serum triglyceride – Mean Change from Baseline to Week 8		
14.2.2	Summary of Serum Lipid Panel – Mean Change from Baseline to Week 8		
14.2.3	Summary of Liver Enzymes (ALT, AST) – Mean Change from Baseline to Week 8		
14.3	Safety Data		
14.3.1	Display of Adverse Events		
14.3.1.1	Number of Treatment-Emergent Adverse Events by System Organ Class and Preferred Term (Safety Analysis Set)		
14.3.1.2	Number of Subjects with Treatment-emergent Adverse Events by System Organ Class and Preferred Term (Safety Analysis Set)		
14.3.1.3	Number of Subjects with Treatment-emergent Adverse Events by System Organ Class, Preferred Term, and Intensity (Safety Analysis Set)		
14.3.1.4	Number of Subjects with Treatment-emergent Adverse Events by System Organ Class, Preferred Term, and Relationship (Safety Analysis Set)		
14.3.1.5	Number of Subjects with Treatment-emergent Serious Adverse Events by System Organ Class and Preferred Term (Safety Analysis Set)		
14.3.1.6	Number of Subjects with Treatment-emergent Adverse Events Leading to Study Discontinuation by System Organ Class and Preferred Term (Safety Analysis Set)		
14.3.2	Listings of Serious and Significant Adverse Events		
14.3.3	Narratives of Serious and Certain Other Significant Adverse Events		
14.3.4	Abnormal Laboratory Value Listing (Each Subject)		
14.3.4.1	Summary of Hematology by Visit (Safety Analysis Set)		
14.3.4.2	Hematology – Shift from Baseline by Visit (Safety Analysis Set)		
14.3.4.3	Summary of Serum Chemistry by Visit (Safety Analysis Set)		
14.3.4.4	Serum Chemistry – Shift from Baseline by Visit (Safety Analysis Set)		
14.3.4.5	Summary of Vital Signs by Visit (Safety Analysis Set)		
14.3.4.6	Summary of Electrocardiogram Results by Visit (Safety Analysis Set)		
14.3.4.7	Shift from Baseline in Electrocardiogram Finding and Overall Impression by Visit (Safety Analysis Set)		
14.3.4.8	Abnormal QTc Interval (ms) by Visit (Safety Analysis Set)		

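### Protocol 12.2.1 opens a new adverse event record at every change of grade, and SAP Table 14.3.1.1 counts events without linking them, so a fluctuating episode is counted more than once

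*Combined protocol and SAP*

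**What the plan says.** **Recording.** Protocol 12.2.1 states: "Any change in severity of signs and symptoms over a number of days will be captured by recording a new AE". The new record takes the changed grade and the date of the change. Direction is not restricted. The one limit concerns changes within a day, for which "the maximum intensity for the event should be noted for that day".

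**Counting.** SAP 15.1 lists Table 14.3.1.1 as "Number of Treatment-Emergent Adverse Events by System Organ Class and Preferred Term (Safety Analysis Set)". Table 14.3.1.2 is a different display: "Number of Subjects with Treatment-emergent Adverse Events by System Organ Class and Preferred Term (Safety Analysis Set)". Tables 14.3.1.3 to 14.3.1.6 also count subjects. SAP 13.1 says that the severity display is "presented based on the maximum severity of a specific AE for a subject". Neither document gives a rule for linking or collapsing records of one episode.

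**Treatment emergence.** Protocol 13.1.4 uses timing alone: "defined as AEs occurring from the time of first dose through 7 days after the last dose of study medication". The SAP definition (section 4, Definitions) has a timing limb as well and adds a second limb for an event "already present prior to the first dose of study drug and becomes more severe post-dose".

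**Start of collection.** Protocol 8.8.2.10 records adverse events from informed consent, Protocol 12.1 includes the screening period, and SAP 13.1 reports from signature of the consent form. Protocol 12.3 starts collection at the first dose, and the schedule of assessments (Table 1 in both documents) first marks adverse event review at Baseline.

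**The concern.** The recording rule suits day-by-day grade capture but not counting. If each change of grade is a separate record and the table counts records, its numbers depend partly on how much an episode fluctuates, not only on how many episodes occurred. An episode that steps down as it resolves adds to the count in the same way as one that worsens.

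This matters most for gastrointestinal events, which the protocol's account of prior studies (4.2.1) presents repeatedly, diarrhea above all. The study has one arm, so no control count is inflated in the same way to set beside it. Protocol 13.1.3 says that the results will be used to design later studies.

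A second question follows from the same rule. A new record opened after dosing has a post-dose date even when it only documents the easing of something recorded before dosing. Its status then depends on which limb of the definition is applied.

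**Working it through.** The plan states no figure on this point, so there is nothing to reproduce. The check applies the stated rule to example grade paths.

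**Step 1: records per episode.** Under Protocol 12.2.1, records = 1 + number of day-to-day grade changes.

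- Grade 1-2-1: 1 + 2 = 3.
- Grade 1-2-3-2-1: 1 + 4 = 5.

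**Step 2: classify the records.** The third column takes each record's date literally (first dose to 7 days after the last dose). The last column collapses records to one episode and admits an episode that began before dosing only if it worsens.

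| Grade path | Records | Counted by date alone | Counted after collapsing, worsening only |
|---|---|---|---|
| On treatment, constant grade | 1 | 1 | 1 |
| On treatment, 1-2-1 | 3 | 3 | 1 |
| On treatment, 1-2-3-2-1 | 5 | 5 | 1 |
| Pre-dose 1, then 2 after dosing | 2 | 1 | 1 |
| Pre-dose 2, then 1 after dosing | 2 | 1 | 0 |
| Pre-dose 3, then 2 and 1 after dosing | 3 | 2 | 0 |

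Rows 2 and 3 depend only on the recording rule and the event-count table. The last two rows also need a pre-dose record to exist and the date to override the second limb of the SAP definition.

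**Step 3: inflation of the total event count.** Let f be the share of episodes that change grade and c the number of changes in each such episode. Then inflation = 1 + f × c. Both inputs are assumptions, because the documents give neither.

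| f | c = 1 | c = 2 |
|---|---|---|
| 0.10 | 1 + 0.10 = 1.10 | 1 + 0.20 = 1.20 |
| 0.25 | 1 + 0.25 = 1.25 | 1 + 0.50 = 1.50 |
| 0.50 | 1 + 0.50 = 1.50 | 1 + 1.00 = 2.00 |

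**Step 4: which outputs are affected.** A subject with three records of one preferred term is still one subject, so splitting alone adds nothing to Tables 14.3.1.2 to 14.3.1.6. Taking the maximum severity per subject and event removes the repeats from the severity display. Table 14.3.1.1 has no such protection.

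**The case against.** The strongest reply is that little is at stake. Protocol section 11 assesses safety by proportions of subjects, the overall summary in SAP 13.1 gives numbers and percentages of subjects, and the severity display uses the maximum. Only one descriptive table is exposed, in a pilot whose sample size does not rest on a hypothesis test. Listing 16.2.7.1 lets a reader see that consecutive records belong together. This stands as a limit on the scope. It does not repair Table 14.3.1.1, because the maximum-severity rule is stated only for the severity display and the data items named in Protocol 12.3 include no link between records.

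A reader might infer three stronger things that the documents do not support.

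- **That easing of a pre-dose event is definitely counted as treatment-emergent, so that the subject tables are inflated too.** One such subject would add 1/40 = 2.5 or 1/20 = 5 percentage points at the sample sizes in Protocol 13.1.3 and SAP 8.1. The SAP's second limb names only worsening for events already present, and it would be redundant if any post-dose change qualified by date. The route also needs a pre-dose record, which Protocol 12.3 and the schedule do not provide for. In addition, Protocol 12.1 names exacerbation of an existing condition as an adverse event, not improvement. What stands is that, if pre-dose events are recorded, the second limb cannot be applied reliably unless the post-dose record is tied to the earlier one.
- **That onset dates move to the higher dose after Week 4.** No adverse event display by dose period is specified, and the first record keeps its own date.
- **That the diarrhea rates in Protocol 4.2.1 give the number of surplus events.** The 9% and 21% come from 500 mg tid and 750 mg bid, both 1500 mg/day. That is three to six times the 250 to 500 mg/day used here. The number of grade changes per episode would still have to be assumed.

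**Conclusion.** The defect is real but confined to event counts. A stated recording rule combined with a stated table gives more than one count for a single fluctuating episode: 3 for Grade 1-2-1 and 5 for Grade 1-2-3-2-1. This follows from the text, provided sites record as instructed and the table is programmed from the records.

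The effect on the whole table cannot be computed. The factors of 1.1 to 2.0 are illustrations under assumed rates of grade change, not estimates.

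The status of a pre-dose adverse event that eases after dosing is unresolved. The date alone would include it, and the SAP's second limb points to excluding it. The documents also disagree on whether such an event would be recorded at all. This part is an ambiguity to close, not a demonstrated miscount.

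**What to change.** Keep the capture of grade changes in Protocol 12.2.1. In SAP 13.1, add:

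1. Records in the same subject with the same preferred term are collapsed into one episode when a record starts on the end date of the previous record or on the day after. The episode takes the first onset date and the maximum severity.
2. Table 14.3.1.1 counts episodes.
3. An episode that began before the first dose is treatment-emergent only if its on-treatment grade exceeds its highest pre-dose grade. The timing-only definition in Protocol 13.1.4 and the synopsis is aligned with this.

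Reconcile the start of adverse event collection: Protocol 8.8.2.10, Protocol 12.1 and SAP 13.1 on one side, Protocol 12.3 and the schedule of assessments on the other.

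The cost is a few lines of SAP text and a short derivation before database lock, with a link field on the adverse event page as an option. It adds no burden for subjects. The downside is small: two distinct events of the same term one day apart may be merged.
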